### 9.3 Tertiary

**Clinical:** Clinical improvement: will be evaluated by comparing the following parameters between the groups:

- Incidence of fever ( $>38^{\circ}\text{C}$ ), persistence, and duration.
- Incidence and duration of other symptoms of illness: chills, myalgia, sore throat, cough, nausea, vomiting, diarrhea, and hemorrhage.
- Death – all causes for study duration

Monitoring the clinical course consistently as opposed to looking at the effect of IFN  $\beta$ -1a on a case-by-case basis should provide additional information to guide indications for therapy during the epidemic and provide detailed surveillance data during this public health emergency.

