**Synopsis**

Product provided by:	BiogenIdec Inc.
Investigational Product/ Drug Product:	Interferon beta-1a (IFN $\beta$ -1a)
Title of the Study:	A Pilot Study to Evaluate the Safety and Efficacy of IFN $\beta$ -1a in the Treatment of Patients Presenting with Ebola Virus Illness.
Development phase:	I/II
Sponsor-Investigator:	[name] [name]
Collaborator:	[name]
Planned Study Period:	January/February 2015 to April/May 2015
Primary Objective:	To evaluate the effectiveness of IFN $\beta$ -1a on viremia in peripheral blood
Primary Endpoint:	Viral load reduction/clearance: Reduction and/or clearance in copies/mL of viral RNA from day 1 to day 14 and, if applicable, 30 days after the last dose
Secondary Objectives:	To evaluate the safety of IFN $\beta$ -1a in the treatment of Ebola virus disease
Secondary Endpoints	
Occurrence and severity of adverse event; time to onset from the initial dose, duration (number of days), severity, and seriousness of solicited and non-solicited injection site reactions and systemic adverse events occurring up to 7 days after the last injection. Occurrence, nature, time to onset from the initial dose, duration, severity, relationship to injection of SAEs throughout the trial, and up to 30 days post-treatment.
 
The frequency of clinically important (moderate or severe) adverse events will be compared between the IFN <math>\beta</math>-1a treatment group and the group receiving usual standard of care.
 
The frequency of serious adverse events will be compared between the groups.

Tertiary Objectives	
To evaluate the effect of IFN <math>\beta</math>-1a therapy on preventing Ebola virus disease progression and/or on resolution of disease.
 
To assess effects on disease symptoms and survival.

Tertiary Endpoints	
Clinical improvement will be evaluated by comparing the following parameters between the groups:
 
Days in treatment centre
 
Days of symptom manifestation: hemorrhage (as IFN <math>\beta</math>-1a may cause fever, myalgia, sore throat, headache, nausea, vomiting, and diarrhea similar to that associated with ebola virus infection, these adverse events will be recorded but not used in the analysis of efficacy).

	Death – all causes for study duration

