#### **Adverse Events**

This section is extracted from the product monograph and is supplementary information to that provided in section 2.3 of the protocol. The side effects listed are based on a phase 3 study with 9 or 15  $\mu$ g of IFN  $\beta$ -1a given three times a week for 24-48 weeks. Since IFN  $\beta$ -1a is given for 10 days in this study, the safety information, listed in section 2.3 for 10 days of therapy, may be more relevant.

The most common adverse events of AVONEX reported in placebo-controlled studies (IM administration) are listed below with the incidence in placebo-treated multiple sclerosis patients listed first and AVONEX-treated multiple sclerosis patients listed second: headache (55%, 58%), flu-like symptoms (29%, 49%), pain (21%, 23%), asthenia (18%, 24%), fever (9%, 20%), chills (5%, 19%), abdominal pain (6%, 8%), injection site pain (6%, 8%), infection (4%, 7%), injection site inflammation (2%, 6%), chest pain (2%, 5%), injection site reaction (1%, 3%), toothache

(1%, 3%), depression (14%, 18%), dizziness (12%, 14%), upper respiratory tract infection (12%, 14%), sinusitis (12%, 14%), bronchitis (5%, 8%), nausea (19%, 23%), myalgia (22%, 29%), arthralgia (6%, 9%), urinary tract infection (15%, 17%), urine constituents abnormal (0%, 3%), alopecia (2%, 4%), eye disorder (2%, 4%), injection site ecchymosis (4%, 6%), anemia (1%, 4%), migraine (3%, 5%), vasodilation (0%, 2%). As some of these symptoms may occur following virus infection, it may be difficult to know whether they are due to the administration of IFN  $\beta$ -1a or the patient's underlying condition

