## 10.2 Statistical analyses and methods

Demographics, and underlying conditions will be described by means and standard deviation for continuous variables, by median and interquartile range for ordinal or count variables, and by frequencies and percentages for categorical variables. Endpoints will be described and compared between treatment and usual standard of care groups using cross-tabulation tables and Fisher's Exact test for categorical variables, t-test for normally distributed continuous variables and Wilcoxon non-parametric test for non-normally distributed continuous or ordinal variables.

Safety variables such as fever will be considered in three different formats:

1. As ordinal, representing various levels of severity of the symptom. For instance, fever will be described as "none", "mild", "moderate", or "severe".
2. As binary, considering only the presence vs. the absence of the symptom.
3. As binary, considering the most serious expression of the symptom. For instance by grouping "moderate" and "severe" together.

Separate analyses for time periods of 0-3, 4-7, and 8-10 days will be conducted. For each of these time periods the most severe report of the AE for each participant will be counted.

Adverse Events and Serious Adverse Events will be considered in two ways: presence of any event and presence of any event related to the treatment.

Symptoms will be assessed as a repeated measure using GEE modelling.

Survival will be analyzed using a Kaplan-Meier curve and Cox-proportional hazard modeling with 2 week and 1 month survival rates determined.

Viral clearance will be analyzed as binary variables for detection (presence) or non-detection (absence) as well as continuous variables where applicable (e.g. quantitative RT-PCR measurements).

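### The Synopsis and section 9.3 give conflicting tertiary efficacy lists, and 9.3 counts six symptoms that the Synopsis excludes because the drug may cause them

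*Protocol*

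**What the plan says.** The protocol defines the tertiary clinical endpoints twice.

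The Synopsis lists three: days in the treatment centre, a symptom measure, and death from any cause. The symptom measure is "Days of symptom manifestation: hemorrhage". The same entry gives the reason for stopping there: the drug "may cause fever, myalgia, sore throat, headache, nausea, vomiting, and diarrhea similar to that associated with ebola virus infection", and "these adverse events will be recorded but not used in the analysis of efficacy".

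Section 9.3 opens with "Clinical improvement: will be evaluated by comparing the following parameters between the groups". It then lists "Incidence of fever" with persistence and duration, followed by "Incidence and duration of other symptoms of illness: chills, myalgia, sore throat, cough, nausea, vomiting, diarrhea, and hemorrhage", and death from any cause. It carries no exclusion and does not mention days in the treatment centre.

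Section 10.2 says that symptoms will be modelled as repeated measures by GEE. It does not say whether this is an efficacy or a safety analysis, or which symptoms enter. The same section treats fever as a safety outcome: "Safety variables such as fever will be considered in three different formats".

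**The concern.** An analyst cannot follow both lists. One who follows 9.3 uses for efficacy what the Synopsis forbids. One who follows the Synopsis leaves out most of 9.3.

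The choice matters because the protocol itself says that the drug can produce symptoms resembling progression of Ebola (section 8.2). If those symptoms count as clinical improvement, a side effect in the treated group reads as lack of benefit, and a real benefit could be masked. Section 16 makes extension to 100 participants depend on safety and, if the small sample allows, on a trend toward efficacy. With two lists on file, the one used for that judgment could be chosen after the data are seen.

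**Working it through.** The plan has no figure of its own to reproduce here. The 30-50 in section 10.1 is a feasibility number. The check is a comparison of the two lists, followed by a look at direction.

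**Step 1: the lists side by side.**

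| Item | Synopsis | Section 9.3 |
|---|---|---|
| Days in treatment centre | efficacy | absent |
| Hemorrhage | efficacy (days) | efficacy (incidence, duration) |
| Death, all causes | efficacy | efficacy |
| Fever, myalgia, sore throat, nausea, vomiting, diarrhea | excluded by name | efficacy |
| Headache | excluded by name | absent |
| Chills, cough | not mentioned | efficacy |

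Section 9.3 has 9 symptoms: fever plus 8 others. The Synopsis excludes 7 by name, and 6 of these are in 9.3. Of the other 3 in 9.3, the Synopsis keeps only hemorrhage. Following the Synopsis would therefore cut the symptom part of clinical improvement from 9 items to 1.

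**Step 2: direction, from the protocol's own rates.** Section 8.2 gives adverse event rates in placebo-controlled intramuscular studies in multiple sclerosis. They cover four of the 9.3 symptoms that are in dispute.

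| Symptom | Placebo | Drug | Difference (points) | Ratio |
|---|---|---|---|---|
| Fever | 9% | 20% | +11 | 2.2 |
| Chills | 5% | 19% | +14 | 3.8 |
| Myalgia | 22% | 29% | +7 | 1.3 |
| Nausea | 19% | 23% | +4 | 1.2 |

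All four differences run against the drug. That list gives no rates for vomiting, diarrhea or sore throat.

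**Step 3: how far the size depends on what is not given.** The protocol states no symptom rates for untreated Ebola patients. For illustration, assume an untreated incidence pc between 20% and 90%, no antiviral effect, and a drug-induced symptom that arises independently of the disease. Then:

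a = (p_drug − p_placebo) / (1 − p_placebo)

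spurious excess = (1 − pc) × a

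For fever, a = (0.20 − 0.09) / 0.91 = 0.121. At pc = 50% the excess is 0.5 × 0.121 = 0.060, or 6.0 points.

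| Symptom | a | pc 20% | pc 50% | pc 80% | pc 90% |
|---|---|---|---|---|---|
| Fever | 0.121 | 9.7 | 6.0 | 2.4 | 1.2 |
| Chills | 0.147 | 11.8 | 7.4 | 2.9 | 1.5 |
| Myalgia | 0.090 | 7.2 | 4.5 | 1.8 | 0.9 |
| Nausea | 0.049 | 4.0 | 2.5 | 1.0 | 0.5 |

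Under these assumptions the sign is always against the drug, while the size runs from 0.5 to 11.8 points. Fever, myalgia, nausea or vomiting, and diarrhea are part of the case definition in section 5.2. Untreated incidence may therefore be high and the excess in incidence small. Duration, which 9.3 also counts, has no such ceiling and may be the more exposed measure.

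**The case against.** Several objections limit the point.

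- **The size does not carry over.** The section 8.2 rates come from intramuscular use in multiple sclerosis. The two studies in section 2.2 dosed once weekly for years. This trial gives daily subcutaneous injections for up to 10 days to acutely ill patients. A reader might infer a built-in excess of 4 to 20 points from the section 8.2 list. The documents do not support that. The 20 is flu-like symptoms (29% v 49%), which is not a 9.3 item, and the illustration above shows how strongly the excess depends on an unstated untreated rate. This objection stands.
- **The net direction is not certain.** A reader might conclude that the comparison is biased against the drug. Section 8.2 allows acetaminophen or ibuprofen before injection for flu-like symptoms, which could lower fever in treated patients only. The comparison group is non-randomised and drawn partly from retrospective records with expected gaps. The direction is expected, not established.
- **Dual use of fever is not itself an error.** Fever can be recorded both for safety and for clinical course. The defect is that the two lists disagree on whether it is efficacy evidence.
- **The GEE is not labelled as efficacy.** Section 10.2 also uses the word symptom in describing its safety formats. It would be wrong to say that the plan commits to an efficacy GEE on the excluded symptoms. It simply does not say.
- **The stakes are limited.** These are tertiary endpoints in a pilot sized for feasibility, and no decision rule in the protocol uses symptom counts. This bears on importance, not on whether the conflict exists.

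None of these objections reconciles the Synopsis with 9.3. Nor is the conflict a detail that an analysis plan could settle without overriding one of the two texts.

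**Conclusion.** The conflict is real and lies in current text. Section 9.3 counts as clinical improvement six of the seven symptoms that the Synopsis excludes, adds chills and cough, and omits days in the treatment centre. Section 10.2 does not say which list its GEE serves.

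Following 9.3 may bias the clinical-improvement comparison, with the expected direction against the drug. That direction rests on the Synopsis's own reasoning and, for fever, chills, myalgia and nausea, on the section 8.2 rates. The size in this trial cannot be stated from the document, and antipyretic use may partly offset the effect on fever.

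The importance is moderate. The primary virologic endpoint and all-cause death are unaffected.

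**What to change.** 1. Amend section 9.3 to the Synopsis list: days in treatment centre, days of hemorrhage, and death from any cause.
2. Report fever, myalgia, sore throat, nausea, vomiting and diarrhea as safety or descriptive clinical course only. Do the same for headache where it is recorded; it is not in the daily symptom list of section 6.5.
3. Treat chills the same way. The Synopsis does not name them, so this goes beyond alignment and rests on the 5% v 19% in section 8.2. Assign cough explicitly, since the Synopsis neither keeps nor excludes it.
4. State in section 10.2 that GEE results for the excluded symptoms are not evidence of efficacy.

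These are wording changes, and the symptoms in the section 6.5 list would still be recorded. The cost is statistical. Section 1.1 says that clinically important hemorrhage occurs in a minority of patients, so the one remaining symptom endpoint will be sparse with 30-50 participants and should be reported with that caveat.

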## 10. Biostatistical Considerations

### 10.1 Sample size estimate

There is no expected sample size for this pilot clinical trial as it is to prove feasibility. This study can include any patient who is suspected or proven to be infected with EBOV and has been admitted to the treatment centre. A sample size of 30-50 has been chosen to assess feasibility of running a clinical trial in the setting with a large number of patients and also the feasibility of treating a large number of patients. If successful, a larger clinical trial may be feasible.

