
Statistical Methods and Analyses
	
Endpoints will be described and compared between baseline and day 10, for the treatment group using cross-tabulation tables and Fisher's Exact test for categorical variables, t-test for normally distributed continuous variables, and Wilcoxon non-parametric test for non-normally distributed continuous or ordinal variables. Data collected will be compared with a retrospective analysis of age-matched Ebola-infected individuals who presented with similar symptoms (and viral loads) and who did not receive IFN <math>\beta</math>-1a.

	
Safety variables such as fever will be considered in three different formats:
 

1. As ordinal, representing various levels of severity of the AE. For instance, fever will be described as “none”, “mild”, “moderate” or “severe”.

2. As binary, considering only the presence vs. the absence of the AE.

3. As binary, considering the most serious expression of the AE. For instance by grouping “moderate” and “severe” together.

 
Separate analyses for time periods of 0-3, 4-7 and 8-10 days will be conducted. For each of these time periods the most severe report of the AE for each participant will be counted.
 
Adverse Events and Serious Adverse Events will be considered in two ways: presence of any event and presence of any event related to the treatment.
 
Viral clearance and symptom endpoints will be analyzed as binary variables for detection (presence) or non-detection (absence) as well as continuous variables where applicable (e.g.; quantitative RT-PCR measurements).

--	---

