### **Pre- and post- Clinical Trial:**

The authority to approve a treating physician's access to IFN  $\beta$ -1a for treatment of patients under the Special Access Program, is based on a medical decision for treatment and a discussion between the treating physician and the patient (or the patient's substitute decision maker). The collection of safety and efficacy data for monitoring by the treating physician and reporting to [name] can be done based on the study case report. This will facilitate reporting by the treating physician and allow more specific and consistent reporting to [name].

This component of the study is to provide the ability to have special access to IFN  $\beta$ -1a if indicated clinically while providing consistent monitoring of adverse events and effect of therapy. Considering that some patients may continue to deteriorate despite antivirals or that they may be infected with an antiviral resistant strain, IFN  $\beta$ -1a will be made available to treating physicians for patients for whom the treating physician believes that there may be a benefit to giving IFN  $\beta$ -1a. Consent for treatment with IFN  $\beta$ -1a would be obtained by the treating physician. Monitoring of treatment will be important to ensure that any safety concerns are identified. Monitoring will include collecting information from the patient's chart as well as some research testing of residual samples which would otherwise be discarded. A template of the informed consent form is attached. The comparison group will be the group of patients who have EBOV disease and do not receive IFN  $\beta$ -1a.

Of note, it is recognized that there will likely be missing data on study participants due to retrospective data collection. Collection of data will be based on the clinical course and interventions required in the care of these patients.

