**A. Case definitions for Suspect or Probable Ebola virus infection:****Clinical Criteria for Ebola virus infection**

- One or more clinical findings of illness associated with a history of at least one of the following symptoms:
  - Temperature of  $>38^{\circ}\text{C}$  ( $100.4^{\circ}\text{F}$ ) and/or
  - Myalgia and/or
  - Fatigue and/or
  - Headache and/or
  - Sore throat and/or
  - Nausea or vomiting
  - Diarrhea
  - Hemorrhage

**Confirmed Case:** Ebola virus disease which meets the clinical criteria with laboratory confirmation for the presence of EBOV by PCR (or qRT-PCR) for the presence of viral genome and/or acute/convalescent serology.

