**5.3 Inclusion Criteria**

Only potential patients fulfilling all of the following criteria are eligible for enrolment in this interventional trial.

1. Able to provide informed consent. Substitute decision maker may provide informed consent in cases where the patient is ill and unable to provide informed consent.
2. Aged  $\geq 18$  years and  $< 70$  years of age on the day of inclusion.
3. Is admitted to the treatment centre.
4. Suspect, probable or confirmed EBOV infection as defined above.
5. Symptoms onset  $< 4$  days
6. Is able to comply with all trial procedures.

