### **Baseline Investigations:**

Given that this is an outbreak with limited health care resources available at the different treatment centres, baseline investigations will be resource-dependent and may include

- Fever/temperature measurement
- PCR determination of viremia
- Clinical evaluation of severity of symptoms such as chills, myalgia, sore throat, cough, nausea, diarrhea, hemorrhage

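### Suspected cases can enter the IFN group while comparators are described as Ebola-infected, and no rule requires baseline viral RNA for the efficacy comparison

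*Protocol*

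**What the plan says.** **Who enters.** Criterion 4 of section 5.3 admits "Suspect, probable or confirmed EBOV infection as defined above". Section 10.1 repeats this: "This study can include any patient who is suspected or proven to be infected with EBOV". The suspect or probable definition in section 5.2 is clinical: "One or more clinical findings of illness associated with a history of at least one of the following symptoms". The list includes fever, fatigue, headache and sore throat, and no exposure or laboratory element is required. Laboratory evidence is needed only for a confirmed case.

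**Whether virus is measured at entry.** Under Baseline Investigations, "baseline investigations will be resource-dependent and may include" PCR. Section 6.5 makes blood for virology subject to feasibility and expects missing data.

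**Who the comparators are.** The Synopsis describes a "retrospective analysis of age-matched Ebola-infected individuals who presented with similar symptoms (and viral loads) and who did not receive IFN" β-1a. Section 5 says: "The comparison group will be the group of patients who have EBOV disease and do not receive IFN" β-1a. Section 5 matches on age, sex, days since onset and, where it is known, viral load.

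**What is compared.** Section 10.2 says: "Viral clearance will be analyzed as binary variables for detection (presence) or non-detection (absence"), as well as continuously where possible. It compares endpoints between the treated and usual-care groups, with Fisher's exact test for categorical variables, and plans Kaplan–Meier and Cox analyses of survival. The Synopsis also describes a baseline-to-day-10 comparison within the treated group.

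**What it is for.** The primary objective in section 4 concerns viremia in infected subjects, and section 5 describes patients admitted with EBOV infection. Section 16 bases extension to 100 participants on safety and, if the numbers allow, on an efficacy trend against standard care.

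**The concern.** The objective and the comparator descriptions presuppose infection, but the entry criterion does not. No section requires a positive baseline PCR for the efficacy comparison or says how a treated suspect who proves negative is handled. The exclusions in section 5.4 and the termination categories in section 12 do not cover that case.

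A treated patient who never had Ebola is undetectable on every day tested and does not face Ebola mortality. Set against infected comparators, that patient adds to the apparent benefit whatever the drug does. The comparisons at stake are detection versus non-detection, all-cause death, and the efficacy trend that feeds the extension decision.

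**Working it through.** The protocol gives no figure to reproduce. The 30–50 in section 10.1 is a feasibility number, with no alpha, power, effect size or clearance rate.

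**Inputs from the protocol:** 30 to 50 treated patients, detection as a binary endpoint, and Fisher's exact test between groups.

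**Assumptions not in the protocol:** a share u of IFN patients is uninfected; a share c of infected patients is undetectable at the assessment day, equal in both groups (no drug effect); all comparators are infected; groups are 1:1 and unmatched; the test is two-sided at 0.05.

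**Size of the bias.** The IFN non-detection rate is u + (1−u)c and the comparator rate is c. The difference is u + c − uc − c = u(1−c), which is positive whenever u > 0 and c < 1.

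**False IFN-better rate at u = 20%, by exact enumeration of Fisher's test:**

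| c (comparators) | IFN rate, 0.2 + 0.8c | Excess, 0.2(1−c) | 30 per group | 50 per group |
|---|---|---|---|---|
| 20% | 36% | 16 points | 19.8% | 35.4% |
| 30% | 44% | 14 points | 13.3% | 23.9% |
| 40% | 52% | 12 points | 10.0% | 18.2% |
| 50% | 60% | 10 points | 7.5% | 13.3% |
| 70% | 76% | 6 points | 4.3% | 6.8% |
| 80% | 84% | 4 points | 2.8% | 4.5% |

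With u = 0 the same calculation gives 1.1–1.4% (30 per group) and 1.4–1.8% (50 per group).

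**Sensitivity to u, at c = 30%:** u = 10% gives 4.8% and 7.7%; u = 30% gives 28.5% and 50.5% (30 and 50 per group).

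**Survival.** The algebra is the same. Section 1.1 puts EBOV fatality at 57–90%. If every uninfected patient survived (an assumption) and u = 20%, IFN survival would be inflated by 0.2 × 0.57 = 11.4 points to 0.2 × 0.90 = 18 points.

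**Within-group analysis.** A never-infected patient is negative at baseline and at day 10, so the change is zero. With no such patient changing status, the observed change is (1−u) times the change among infected patients: at u = 20%, four fifths of it. This works against IFN.

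**The case against.** **The analysis set may be defined in a statistical analysis plan.** A reader might infer that the protocol puts unconfirmed patients into the viral-clearance analysis. It does not say so: section 10.2 names no analysis population, and a plan not seen here could restrict the set. What stands is that the mismatch between eligibility and comparators, and between eligibility and the wording of sections 4 and 5, is in the protocol itself.

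**The direction is not uniform.** A reader might infer that the primary endpoint is biased towards IFN throughout. Section 5 calls the study single-arm with a pre/post design, and there the effect is dilution. Section 9.1 also words the endpoint as clearance or reduction from day 1, so a patient with no RNA on day 1 arguably has nothing to clear. The inflation belongs to the between-group comparison of detection status and to survival.

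**Matching on viral load would help.** Enforced with data, it would leave a PCR-negative IFN patient without a comparable infected match. But section 5 makes it conditional on the value being known, so it fails where baseline PCR is missing. The table assumes no matching and overstates the problem to the extent that matching works.

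**The comparators may not all be infected.** No section requires their laboratory confirmation. If a share v were also uninfected, the excess would be (u−v)(1−c), which is smaller and could vanish. The protocol's wording points to v near zero but does not secure it. This is a reason to state one rule for both groups.

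**The error rates are illustrative.** They rest on assumed u, c and group ratio, and shrink when most infected patients have cleared by the assessment day.

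**Conclusion.** The point holds for the between-group comparisons. Followed as written, the protocol can enrol uninfected patients on IFN, compare them with patients described as having Ebola, and count their lack of virus and their survival in the drug's favour. The direction there follows from the algebra if comparators are infected and viral-load matching does not remove the uninfected patients.

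The size cannot be fixed from the protocol. At 20% uninfected, the false IFN-better rate runs from 2.8% to 19.8% with 30 per group and from 4.5% to 35.4% with 50, against about 1.1–1.8% with none. A single figure from that range should not be quoted as the trial's error rate. Nor should a one-sided 2.5% be called the intended level, since the protocol states no alpha and Fisher's test is conservative at these sizes.

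The documents do not support a claim that the whole primary analysis favours IFN, because the pre/post analysis is diluted instead. Under either analysis, a patient without viremia says nothing about the drug's effect on viremia.

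**What to change.** Leave enrolment and treatment unchanged, and add to sections 9 and 10:

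- **Efficacy set.** For the virologic and survival comparisons, the primary set is patients with EBOV RNA detected in the pre-dose day 1 specimen, tested afterwards on residual blood if necessary. The criterion should be RNA and not confirmed-case status, because section 5.2 also allows confirmation by serology.
- **Comparators.** Apply the same laboratory rule at the equivalent time point.
- **Other sets.** Keep all dosed patients for safety, and show survival in all treated patients as a secondary analysis.
- **Reporting.** Give the number left out as RNA-negative and, separately, the number without a pre-dose sample.
- **Consistency.** Reconcile sections 4 and 5, which speak of infected patients, with the Synopsis and sections 5.3 and 10.1, which admit suspects.

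Section 5 already plans testing of residual blood, so the protocol change is mostly wording. The practical cost is larger. With 20% unconfirmed, the efficacy set falls from 30–50 to about 24–40 (30 × 0.8 and 50 × 0.8), and further wherever a pre-dose sample is missing, which is plausible since baseline PCR depends on resources. Patients with a sample may differ from those without, so the restriction can introduce selection of its own. The all-treated survival analysis and the exclusion counts let a reader judge this.
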